Approximately, 84 participants will be randomized in a 2:1 ratio to SAR442970 150 mg or matching placebo. Randomization will first be stratified by HS treatment history into 2 major subgroups:

- Biologic and small molecule immunosuppressive-naïve subgroup.
- TNF-experienced subgroup.

The biologic and small molecule immunosuppressive-naïve subgroup is composed of participants who have never received biologic therapies, such as anti-TNF therapy, anti-interleukin (IL)17, anti-IL1, anti-IL36, or anti-IL23, or small molecule immunosuppressive therapies, such as Janus kinase/tyrosine kinase (JAK/TYK) inhibitors. The recruitment target for the biologic and small molecule immunosuppressive-naïve subgroup is approximately 66 participants. Randomization will be further stratified by Hurley Stage (II or III). Within the biologic and small molecule immunosuppressive-naïve subgroup, the number of participants with Hurley Stage III is not to exceed more than 50% in order to recruit a population with the desired disease severity.

The TNF-experienced subgroup is composed of participants who experienced at least one of the following scenarios after receiving a single anti-TNF therapy (adalimumab, certolizumab pegol, etanercept, golimumab, infliximab, etc) for at least 12 weeks as assessed by the Investigator through participant interview and review of medical history:

- Participants who had a complete response to anti-TNF therapy for HS per Investigator discretion and subsequently lost response, or
- Participants who had a partial response to anti-TNF therapy for HS per Investigator discretion, or
- Participants who did not achieve a partial response to anti-TNF therapy for HS per Investigator discretion, or
- Participants who stopped using anti-TNF therapy due to reasons other than an adverse event (AE) (ie, insurance or access or other reasons) (8, 9).

For the TNF-experienced subgroup, if participants have received more than 1 anti-TNF therapy for HS, they are not eligible for participation. Participants that have experienced an AE related to anti-TNF therapy (examples include, but are not limited to, serum sickness or anaphylaxis) that would contraindicate re-administration of an anti-TNF class therapy will be excluded. The recruitment target for the TNF-experienced subgroup is approximately 18 participants.

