| Secondary 

• To evaluate the efficacy and safety of SAR442970 in the biologic and small molecule immunosuppressive-naïve subgroup of participants with HS

• To evaluate the effect of SAR442970 on pain in the biologic and small molecule immunosuppressive-naïve subgroup of participants with HS

• To evaluate the pharmacokinetics (PK) of SAR442970 and anti-drug antibodies to SAR442970 in the biologic and small molecule immunosuppressive-naïve subgroup of participants with HS

 | 

• Time to onset of achieving HiSCR50

• Percentage of participants achieving HiSCR75 (defined as ≥75% reduction from Baseline in the total AN count, with no increase from Baseline in abscess or draining tunnel count) at Week 16

• Percentage of participants achieving HiSCR90 (defined as ≥90% reduction from Baseline in the total AN count, with no increase from Baseline in abscess or draining tunnel count) at Week 16

• Percentage of participants who experience improvement by at least one International Hidradenitis Suppurativa Severity Score System (IHS4) stage at Week 16 (See also Section 8.2.1.3 for definition of IHS4)

• Change in absolute score from Baseline in IHS4 at Week 16

• Percentage of participants who experience a flare, defined as at least a 25% increase in AN count (with a minimum increase of 2) relative to Baseline at Week 16 (See also Section 8.2.1.4 for definition of flare)

• Percentage of participants achieving IHS4-55 at Week 16 (defined as achievement of a 55% reduction in IHS4 score from Baseline)

• Incidence of treatment-emergent adverse events (TEAEs), adverse events of special interest (AESIs), and serious adverse events (SAEs) including local reactions

• Incidence of potentially clinically significant abnormalities in laboratory tests, vital signs, and electrocardiograms

• Percentage of participants achieving at least 30% reduction and at least 1 unit reduction from Baseline in weekly average of daily [REDACTED]
[REDACTED]
[REDACTED]
[REDACTED]
[REDACTED]

• Serum SAR442970 concentrations throughout the study

• Incidence of anti-SAR442970 antibody positive response throughout the study

 |

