#### **Events meeting the AE definition**

- Any abnormal laboratory test results (hematology, clinical chemistry, or urinalysis) or other safety assessments (eg, ECG, radiological scans, vital signs measurements), including those that worsen from Baseline, considered clinically significant in the medical and scientific judgment of the Investigator (ie, not related to progression of underlying disease, or more severe than expected for the participant's condition), eg:
  - Symptomatic and/or
  - Requiring either corrective treatment or consultation, and/or
  - Leading to IMP discontinuation or modification of dosing, and/or

- Fulfilling a seriousness criterion, and/or
- Defined as an AESI.
- Exacerbation of a chronic or intermittent pre-existing condition including either an increase in frequency and/or intensity of the condition.
- New condition detected or diagnosed after study intervention administration even though it may have been present before the start of the study.
- Signs, symptoms, or the clinical sequelae of a suspected drug-drug interaction.
- Signs, symptoms, or the clinical sequelae of a suspected overdose of either study intervention or a concomitant medication.
- Signs, symptoms, or the clinical sequelae of any medication errors, misuse, and abuse with the IMP.
- Lack of efficacy or failure of expected pharmacological action per se will not be reported as an AE or SAE. Such instances will be captured in the efficacy assessments. However, the signs, symptoms, and/or clinical sequelae resulting from lack of efficacy will be reported as AE or SAE if they fulfil the definition of an AE or SAE.
- The signs, symptoms, and/or clinical sequelae resulting from lack of efficacy will be reported as an AE or SAE if they fulfil the definition of an AE or SAE. Lack of efficacy or failure of expected pharmacological action also constitutes an AE or SAE.

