#### **Events NOT meeting the AE definition**

- Any abnormal laboratory findings or other abnormal safety assessments that are associated with the underlying disease, unless judged by the Investigator to be more severe than expected for the participant's condition.
- The disease/disorder being studied or expected progression, signs, or symptoms of the disease/disorder being studied, unless more severe than expected for the participant's condition.
- Medical or surgical procedure (eg, endoscopy, appendectomy): the condition that leads to the procedure is the AE.
- Situations in which an untoward medical occurrence did not occur (social and/or convenience admission to a hospital).
- Anticipated day-to-day fluctuations of pre-existing disease(s) or condition(s) present or detected at the start of the study that do not worsen.

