2.7.2 Adverse events

General common rules for adverse events

All adverse events (AEs) will be coded to a preferred term (PT) and associated primary system organ class (SOC) using the Medical Dictionary for Regulatory Activities (MedDRA) version currently in effect at Sanofi at the time of database lock.

The AEs will be analyzed in the following 3 categories:

- Pre-treatment AEs: AEs that developed, worsened, or became serious during the pre-treatment period
- Treatment-emergent adverse events (TEAEs): AEs that developed, worsened, or became serious during the treatment-emergent period
- Post-treatment AEs: AEs that developed, worsened, or became serious during the post-treatment period

Similarly, the deaths will be analyzed in the pre-treatment, treatment-emergent period and post-treatment periods.

The primary AE analyses will be on TEAEs. Pre-treatment and post-treatment AEs will be described separately.

An AE with incomplete or missing date/time of onset (occurrence, worsening, or becoming serious) will be classified as a TEAE unless there is definitive information to determine it is a pre-treatment or a post-treatment AE.

If the assessment of the relationship to IMP is missing for an AE, this AE will be assumed as related to IMP. Missing severity will be left as missing.

Multiple occurrences of the same event in the same participant will be counted only once in the tables within a treatment phase.

The AE tables will be sorted as indicated in [Table 6](#).

Table 6 - Sorting of AE tables

AE presentation	Sorting rules
SOC and PT	By the internationally agreed SOC order and decreasing frequency of PTs ^a ,

a Sorting will be based on the SAR442970 intervention group

Analysis of all adverse events

The overview of TEAEs with the details below will be generated:

- Any TEAE
- Any treatment-emergent SAE

- Any severe TEAE
- TEAE leading to death
- Any TEAE leading to permanent intervention discontinuation
- Any treatment-emergent AESI
- Any TEAE related to IMP as per the Investigator's judgment

The AE summaries of [Table 7](#) will be generated with number (%) of participants experiencing at least one event and sorted by the internationally agreed SOC order and decreasing frequency of PTs. Sorting will be based on experimental study drug intervention group (see [Table 6](#)).

Table 7 - Analyses of adverse events

Type of AE	MedDRA levels
All TEAE	Primary SOC and PT
TEAE related to IMP as per Investigator's judgement	Primary SOC and PT

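### The protocol's AE definition gives opposite rules on whether lack of efficacy is an AE, so TEAE incidence could be inflated inconsistently across sites

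*Protocol*

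**What the plan says.** Protocol Section 10.3.1, in the list of events that meet the AE definition, has two consecutive bullets on this subject.

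- The first states "Lack of efficacy or failure of expected pharmacological action per se will not be reported as an AE or SAE" and then "Such instances will be captured in the efficacy assessments". It adds that resulting signs, symptoms or sequelae are reportable if they are AEs in their own right.
- The second repeats that point about signs and sequelae and then ends "Lack of efficacy or failure of expected pharmacological action also constitutes an AE or SAE".

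The list that follows, of events that do not meet the definition, includes the disease under study and its "expected progression, signs, or symptoms of the disease/disorder being studied, unless more severe than expected" for the participant's condition.

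The definition feeds a secondary endpoint in protocol Table 2: "Incidence of treatment-emergent adverse events (TEAEs), adverse events of special interest (AESIs), and serious adverse events (SAEs) including local reactions". SAP Section 2.7.2 defines TEAEs as "AEs that developed, worsened, or became serious during the treatment-emergent period", with no exception for lack of efficacy. It also states "If the assessment of the relationship to IMP is missing for an AE, this AE will be assumed as related to IMP". SAP Table 7 tabulates TEAEs leading to permanent discontinuation separately.

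**The concern.** The two bullets share a subject and give opposite instructions. Neither is marked as an alternative or limited to a setting. The near-repetition of the sentence on signs and sequelae suggests that two alternative template texts were both left in.

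A site that follows the second bullet can enter lack of efficacy as an AE, and nothing in the SAP removes it. Three outputs are exposed:

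- overall TEAE incidence;
- TEAEs leading to permanent discontinuation, because both documents recognise lack of efficacy as a reason for stopping study intervention;
- TEAEs related to IMP, wherever causality is left blank and the SAP default applies.

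Because practice could differ by site, the result is partly noise. If the drug works, it is also a bias: more such entries would arise on placebo, which would hide an AE excess on active in the crude comparison.

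**Working it through.** **Does other text settle the conflict?**

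| Text | Effect |
|---|---|
| Protocol 10.3.1, first bullet | Lack of efficacy is not an AE; it is handled as efficacy data |
| Protocol 10.3.1, second bullet | Lack of efficacy is an AE or SAE |
| Protocol 10.3.1, events not meeting the definition | Leans to the first bullet but does not mention lack of efficacy |
| SAP 2.7.2 | Counts whatever is recorded as an AE in the treatment-emergent period |

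The conflict is not resolved anywhere.

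**How large could the effect be?** The documents give no figure to reproduce, so this is a ceiling and not an estimate.

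Inputs:

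- Allocation: "Approximately, 84 participants will be randomized in a 2:1 ratio to SAR442970 150 mg or matching placebo" (protocol synopsis). The naïve subgroup target is 66, so about 44 active and 22 placebo.
- Placebo response: the SAP 2.2.2 prior is beta(2.1; 4.9), with mean 2.1 / (2.1 + 4.9) = 30%. Non-response is 70%.
- Active response: the planning rate is redacted. As an assumption, use the 42% and 59% adalimumab HiSCR50 rates cited in protocol Section 2.1.1 from two Phase 3 trials. Non-response is then 58% to 41%.

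Expected non-responders = n × (1 − response rate):

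- Placebo: 22 × 0.70 = 15.4
- Active: 44 × 0.58 = 25.5, down to 44 × 0.41 = 18.0

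If every non-response were recorded as an AE and nobody had any other AE, the placebo excess would be:

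- 70 − 58 = 12 points
- 70 − 41 = 29 points

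**Allowing for participants who already have another AE.** Let a be the other-AE rate and r the response rate. If the two are independent, the share with any AE is 1 − (1 − a) × r. Take a = 60% in both arms (assumed), so there is no true difference:

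- Placebo: 1 − 0.40 × 0.30 = 88.0%
- Active: 1 − 0.40 × 0.42 = 83.2%, or 1 − 0.40 × 0.59 = 76.4%
- Spurious placebo excess: 4.8 to 11.6 points

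Now take other-AE rates of 60% active and 50% placebo (assumed), a true +10 points on active:

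- Placebo: 1 − 0.50 × 0.30 = 85.0%
- Active: 83.2% to 76.4%, as above
- Apparent difference, active minus placebo: −1.8 to −8.6 points, so at the ceiling the sign reverses

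If active response were also 30%, active would be 1 − 0.40 × 0.30 = 88.0%. The +10 would shrink to +3 but keep its sign.

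**The case against.** The strongest reply accepts the drafting conflict and disputes its consequence. Several parts of that reply stand.

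- **A reader might infer that every non-responder would have an AE.** The documents do not support that. The bullet speaks of lack of efficacy, not of HiSCR50 non-response. HiSCR50 is calculated from eCRF lesion counts (protocol 8.2.1.2), and non-responders include participants with missing data or composite intercurrent events (protocol Table 3). The exclusion for expected disease course also discourages wholesale recording.
- **A reader might infer a flood of extra SAEs.** An SAE must still meet a seriousness criterion (protocol 10.3.2). Bare non-response rarely would, and a sequela that does so and qualifies as an AE is reportable under either bullet.
- **A reader might infer that the drug is bound to look safer.** Both arms are subject to the same rule. The difference between arms arises only if the drug works.
- **Timing weakens a Period A gap.** Week 16 status becomes known at about the first open-label dose, when SAP 2.1 closes the Period A treatment-emergent window. The only formal classification of response by sites is at Week 20 in the US, after all continuing participants have moved to active drug.
- **The outputs are descriptive.** SAP 2.7 plans no safety testing, and coding by SOC and PT would make such entries identifiable.

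These points limit the size. They do not remove the contradiction, and the any-TEAE overview row would still absorb whatever was entered.

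**Conclusion.** The contradiction is real, sits in current text, and governs a rule that feeds a secondary endpoint. It should be corrected, but it does not threaten the trial's primary conclusion.

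Its effect on TEAE incidence is unknown and depends on site practice. The only defensible figure is an upper bound of about 12 to 29 points of spurious placebo excess. That bound assumes that every non-response is recorded, that placebo response equals the SAP prior mean, and that the active arm responds like adalimumab in the cited trials. Participants with another AE bring it down, to about 5 to 12 points in the 60% example. With equal response in both arms, recording non-response creates no excess of its own, although it still inflates both rates and compresses a true difference. Any effect on SAE counts should be small.

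**What to change.** 1. In protocol Section 10.3.1, delete the sentence "Lack of efficacy or failure of expected pharmacological action also constitutes an AE or SAE". The rest of that bullet repeats the first bullet and can go with it. Keep the first bullet, which agrees with the list of events not meeting the AE definition.
2. Send sites a short note stating the single rule.
3. Add a line to SAP Section 2.7.2: lack-of-efficacy entries already recorded are identified before database lock, and the TEAE and SAE tables, including TEAEs leading to discontinuation, are shown with and without them. This is needed because the SAP version history dates the first randomization at 11-Jul-2023, so entries under the conflicting text may already exist.

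The cost is small: a protocol amendment with IRB/IEC approval (protocol Section 10.1.1), a site communication, and one extra version of the affected safety tables. Sample size, endpoints and visit schedule are unchanged.

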#### **Events NOT meeting the AE definition**

- Any abnormal laboratory findings or other abnormal safety assessments that are associated with the underlying disease, unless judged by the Investigator to be more severe than expected for the participant's condition.
- The disease/disorder being studied or expected progression, signs, or symptoms of the disease/disorder being studied, unless more severe than expected for the participant's condition.
- Medical or surgical procedure (eg, endoscopy, appendectomy): the condition that leads to the procedure is the AE.
- Situations in which an untoward medical occurrence did not occur (social and/or convenience admission to a hospital).
- Anticipated day-to-day fluctuations of pre-existing disease(s) or condition(s) present or detected at the start of the study that do not worsen.

#### **10.3.2 Definition of SAE**

**An SAE is defined as any untoward medical occurrence that, at any dose, meets one or more of the criteria listed:**

- a) Results in death**
- b) Is life-threatening**

The term *life-threatening* in the definition of *serious* refers to an event in which the participant was at risk of death at the time of the event. It does not refer to an event, which hypothetically might have caused death, if it were more severe.

**c) Requires inpatient hospitalization or prolongation of existing hospitalization**

- In general, hospitalization signifies that the participant has been admitted (usually involving at least an overnight stay) at the hospital or emergency ward for observation and/or treatment that would not have been appropriate in the physician's office or outpatient setting. Complications that occur during hospitalization are AEs. If a complication prolongs hospitalization or fulfills any other serious criteria, the event is serious. When in doubt as to whether hospitalization occurred or was necessary, the AE should be considered serious.
- Hospitalization for elective treatment of a pre-existing condition that did not worsen from Baseline is not considered an AE.

**d) Results in persistent or significant disability/incapacity**

- The term disability means a substantial disruption of a person's ability to conduct normal life functions.
- This definition is not intended to include experiences of relatively minor medical significance such as uncomplicated headache, nausea, vomiting, diarrhea, influenza, and accidental trauma (eg, sprained ankle) that may interfere with or prevent everyday life functions but do not constitute a substantial disruption.

**e) Is a congenital anomaly/birth defect**

**f) Other situations:**

- Medical or scientific judgment should be exercised by the Investigator in deciding whether SAE reporting is appropriate in other situations such as important medical events that may not be immediately life-threatening or result in death or hospitalization but may jeopardize the participant or may require medical or surgical intervention to prevent one of the other outcomes listed in the above definition. These events should usually be considered serious.
- The following list of medically important events is intended to serve as a guideline for determining which condition has to be considered as a medically important event. The list is not intended to be exhaustive:
  - Intensive treatment in an emergency room or at home for:
    - Allergic bronchospasm.
    - Blood dyscrasias (ie, agranulocytosis, aplastic anemia, bone marrow aplasia, myelodysplasia, pancytopenia, etc).
    - Convulsions (seizures, epilepsy, epileptic fit, absence, etc).
  - Development of drug dependence or drug abuse.
  - ALT  $>3 \times$  ULN + total bilirubin  $>2 \times$  ULN or asymptomatic ALT increase  $>10 \times$  ULN.
  - Suicide attempt or any event suggestive of suicidality.

- Syncope, loss of consciousness (except if documented as a consequence of blood sampling).
- Bullous cutaneous eruptions.
- Chronic neurodegenerative diseases (newly diagnosed) or aggravated during the study.

### **10.3.3 Recording and follow-up of AE and/or SAE**

#### **AE and SAE recording**

- When an AE/SAE occurs, it is the responsibility of the Investigator to review all documentation (eg, hospital progress notes, laboratory reports, and diagnostics reports) related to the event.
- The Investigator will then record all relevant AE/SAE information.
- It is **not** acceptable for the Investigator to send photocopies of the participant's medical records to the Sponsor's representative in lieu of completion of the required form.
- There may be instances when copies of medical records for certain cases are requested by the Sponsor's representative. In this case, all participant identifiers, with the exception of the participant number, will be redacted on the copies of the medical records before submission to the Sponsor's representative.
- The Investigator will attempt to establish a diagnosis of the event based on signs, symptoms, and/or other clinical information. Whenever possible, the diagnosis (not the individual signs/symptoms) will be documented as the AE/SAE.

#### **Assessment of intensity**

The Investigator will make an assessment of intensity for each AE and SAE reported during the study and assign it to one of the following categories:

- Mild: A type of adverse event that is usually transient and may require only minimal treatment or therapeutic intervention. The event does not generally interfere with usual activities of daily living.
- Moderate: A type of adverse event that is usually alleviated with additional specific therapeutic intervention. The event interferes with usual activities of daily living, causing discomfort but poses no significant or permanent risk of harm to the research participant.
- Severe: A type of adverse event that interrupts usual activities of daily living, or significantly affects clinical status, or may require intensive therapeutic intervention.

#### **Assessment of causality**

- The Investigator is obligated to assess the relationship between study intervention and each occurrence of each AE/SAE. The Investigator will use clinical judgment to determine the relationship.
- A reasonable possibility of a relationship conveys that there are facts, evidence, and/or arguments to suggest a causal relationship, rather than that a relationship cannot be ruled out.

- Alternative causes, such as underlying disease(s), concomitant therapy, and other risk factors, as well as the temporal relationship of the event to study intervention administration will be considered and investigated.
- For causality assessment, the Investigator will also consult the IB and/or product information, for marketed products.
- The Investigator must review and provide an assessment of causality for each AE/SAE and document this in the medical notes. There may be situations in which an SAE has occurred, and the Investigator has minimal information to include in the initial report to the Sponsor's representative. However, **it is very important that the Investigator always make an assessment of causality for every event before the initial transmission of the SAE data to the Sponsor's representative.**
- The Investigator may change his/her opinion of causality in light of follow-up information and send an SAE follow-up report with the updated causality assessment.
- The causality assessment is one of the criteria used when determining regulatory reporting requirements.

